9.2.3 Evaporative Air Sensitivity

The evaporative air sensitivity of all clinically eligible teeth from Screening will be assessed at Baseline (Visit 2). The evaporative air sensitivity of the two ‘test teeth’ selected at Baseline, followed by the remaining eligible teeth identified at Screening, will be assessed for all randomised subjects at subsequent visits (Visits 3-7).

The evaporative air stimulus will be administered, and subject response recorded, as described in [Section 9.1.5](#). On every occasion, evaporative air assessment will begin a minimum of 5 minutes after the last tactile assessment has been completed (to allow tooth recovery time).

9.2.4 Selection of Test Teeth

On completion of the Baseline clinical assessments, the clinical examiner will select two ‘test teeth’ for each eligible subject, to be evaluated at all subsequent visits. Test teeth will exhibit none of the dentition exclusions and meet all the inclusion criteria for eligible teeth (including Screening and Baseline tactile threshold \leq 20 g; Screening and Baseline Schiff sensitivity score \geq 2).

Test teeth should not be adjacent to each other and preferably in different quadrants.

9.3 Safety and Other Assessments

The following safety assessments will be performed by appropriately trained clinical examiners, at the times and in the order defined in the Study Procedures section of this protocol ([Section 8](#)).

9.3.1 Oral Soft Tissue (OST) Examination

The OST examination will be accomplished by direct observation and palpation, using retraction aids as appropriate, and will include examination of the labial mucosa (including lips), buccal mucosa, and mucogingival folds, gingival mucosa, hard palate, soft palate, tonsillar area, pharyngeal area, tongue, sublingual area, submandibular area

and salivary glands. The results of the examination will be recorded in the CRF as either normal or abnormal with details of any abnormalities. Any abnormality or worsening of a pre-existing condition observed by the clinical examiner or reported by the subject from the OST examination carried out at Screening will be recorded as an AE.

9.3.2 Oral Hard Tissue (OHT) Examination

The OHT examination will be accomplished by direct observation, using retraction aids as appropriate and will identify any grossly carious lesions or signs of erosive wear, enamel irregularities, tooth fracture, gross decay, decalcification and faulty restorations. The presence of any implants, fixed or removable dentures, fixed or removable orthodontic braces/bands, fixed orthodontic retainers, full crowns or veneers will be recorded. Observations will be listed as either absent or present, and conditions noted as present will be described in the CRF. Any change observed by the clinical examiner or reported by the subject from the OHT examination carried out at Screening will be recorded as an AE.

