10 ADVERSE EVENT AND SERIOUS ADVERSE EVENTS

10.1 Definition of an Adverse Event (AE)

An AE is any untoward medical occurrence in a clinical study subject, temporally associated with the use of a study product including any washout or lead-in product (or

medical device), whether or not considered related to the study product, including any washout or lead-in product (or medical device).

NOTE: An AE can therefore be any unfavorable and unintended sign (including an abnormal laboratory finding), symptom, or disease (new or exacerbated) temporally associated with the use of a study product including any washout or lead-in product (or medical device).

Events Meeting the AE Definition:

- Any abnormal laboratory test results (hematology, clinical chemistry, or urinalysis) or other safety assessments (e.g. ECG, radiological scans, vital sign measurements), including those that worsen from baseline, considered clinically significant in the medical and scientific judgment of the investigator (i.e., not related to progression of underlying disease).
- Exacerbation of a chronic or intermittent pre-existing condition including either an increase in frequency and/or intensity of the condition.
- New conditions detected or diagnosed after study product administration even though it may have been present before the start of the study.
- Signs, symptoms, or the clinical sequelae of a suspected drug-drug interaction.
- Signs, symptoms, or the clinical sequelae of a suspected overdose of either study product or a concomitant medication. Overdose per se will not be reported as an AE/SAE unless it is an intentional overdose taken with possible suicidal/self-harming intent. Such overdoses should be reported regardless of sequelae.
- "Lack of efficacy" or "failure of expected pharmacological action" per se will not be reported as an AE. Such instances will be captured in the efficacy assessments. However, the signs, symptoms, and/or clinical sequelae resulting from lack of efficacy will be reported as AE if they fulfill the definition of an AE.

Events NOT meeting the AE definition:

- Any clinically significant abnormal laboratory findings (if applicable) or other abnormal safety assessments which are associated with the underlying disease, unless judged by the investigator to be more severe than expected for the subject's condition.

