- The disease/disorder being studied or expected progression, signs, or symptoms of the disease/disorder being studied, unless more severe than expected for the subject's condition.

- Medical or surgical procedure (e.g. endoscopy, appendectomy) is not the AE. The condition that leads to the procedure is an AE (e.g. appendicitis).
- Situations where an untoward medical occurrence did not occur (social and/or convenience admission to a hospital).
- Anticipated day-to-day fluctuations of pre-existing disease(s) or condition(s) present or detected at the start of the study that do not worsen.

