3.1 Baseline Definition

For all endpoints, the baseline value will be the Day 0 (Visit 2) pre-treatment assessment with a non-missing value.

Unless otherwise stated, if baseline data is missing no derivation will be performed and will be set to missing.

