4.6 Analysis of Safety

4.6.1 Adverse Events and Serious Adverse Events

Safety data will be reported for the Safety Population as per study product received. The safety and oral tolerability of the study products will be monitored over the 8-week treatment period by review of reported AEs and incidents. All AEs will be reviewed by the Clinical Research Scientist or Designee prior to database lock and unblinding and will be coded to a system organ class (SOC) and preferred term (PT) using the Medical Dictionary for Regulatory Activities (MedDRA). AEs will be classified as oral or non-oral on the AE page of the eCRF.

Treatment emergent adverse events (TEAEs) are defined as AEs that occur on or after the first study product application at the Baseline visit (if this date is missing a suitable alternative will be used e.g., date of randomization). AEs with an onset date/time prior to the first study product application will be considered as non-treatment emergent.

The following AE tables and listings will be produced, presented by study product group and overall:

- Table of TEAEs by SOC and PT ([Table 14.3.1.1](#))
- Table of TEAEs by Oral/Non-Oral and PT ([Table 14.3.1.2](#))
- Table of treatment-related TEAEs by Oral/Non-Oral and PT ([Table 14.3.1.3](#))
- Table of treatment-emergent treatment-related SAEs by SOC and PT ([Table 14.3.1.4](#)) [only produced if there are more than 5 SAEs]
- Table of treatment-related non-serious TEAEs by SOC and PT ([Table 14.3.1.5](#)) [only produced if there are more than 5 SAEs]
- Listing of all AEs ([Listing 16.2.7.1](#) randomized subjects; [Listing 16.2.7.2](#) non-randomized subjects)
- Listing of deaths ([Listing 14.3.2.1](#))
- Listing of non-fatal SAEs ([Listing 14.3.2.2](#))
- Listing of TEAEs leading to study or treatment withdrawal ([Listing 14.3.2.3](#))

In the event there is nothing to report, a null table or listing will be produced.

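### Protocol 9.3.2 makes any hard-tissue change since Screening an adverse event, whatever its direction, which contradicts the AE definition in 10.1 and can slightly inflate the AE tables

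*Protocol*

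**What the plan says.** Protocol 9.3.2 covers decay, erosive wear, fracture, decalcification and faulty restorations, and also the presence of implants, dentures, orthodontic appliances, crowns and veneers. On scoring it says: "Observations will be listed as either absent or present, and conditions noted as present will be described in the CRF". The rule that turns these scores into AEs comes next: "Any change observed by the clinical examiner or reported by the subject from the OHT examination carried out at Screening will be recorded". What is recorded is an AE, and the sentence sets no condition on direction, severity or clinical relevance.

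Three other places bear on this rule:

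- **Protocol 9.3.1 (soft tissue).** The corresponding trigger is "Any abnormality or worsening of a pre-existing condition observed by the clinical examiner or reported by the subject", which is limited to adverse findings.
- **Protocol 10.1 (AE definition).** An AE is an untoward occurrence, and the note adds: "An AE can therefore be any unfavorable and unintended sign". On dental work and similar care it says: "Medical or surgical procedure (e.g. endoscopy, appendectomy) is not the AE". The condition that led to the procedure is the AE. Fluctuations of pre-existing conditions that do not worsen are listed as not being AEs.
- **SAP 4.6.1 (treatment emergence).** Treatment-emergent AEs are "defined as AEs that occur on or after the first study product application at the Baseline visit". Protocol 12.2.7 uses the same onset rule.

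**The concern.** Sections 9.3.2 and 10.1 give different answers for the same observation. Site staff completing the Day 56 OHT page have a specific instruction that says record, and a general definition that says the finding is not an AE. Different staff could reasonably follow different sections.

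The safety tables are affected. Treatment-emergent AEs are the only safety endpoint in Protocol Table 3-1. OHT results are otherwise only listed; SAP 4.6.2 tabulates the soft-tissue results but not the hard-tissue ones. The AE tables are therefore the only planned per-arm summary in which an OHT change would appear, and under 9.3.2 they could mix improvement and treatment with harm.

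**Working it through.** The documents give no expected number of OHT changes or AEs, so there is no figure of the plan's own to reproduce. The check sets the rules side by side and then works out the scale per affected subject.

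**1. Possible changes under each rule**

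| Change from Screening OHT | 9.3.2 as written | 10.1 | 9.3.1 wording, if applied to OHT |
|---|---|---|---|
| Abnormality absent, later present | AE | AE (new condition) | AE |
| Abnormality present, later worse | AE | AE (exacerbation) | AE |
| Abnormality present, later absent (improved, repaired or read differently) | AE | Not an AE | Not an AE |
| Crown absent, later present on a non-test tooth | AE (the crown) | The crown is not the AE; the condition behind it is | Not an AE in itself |

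The rules agree on the first two rows. The contradiction lies in the last two.

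**2. Whether those rows can occur**

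- Exclusion criterion 21 bars crowned, veneered or carious teeth only as test teeth, so other teeth can carry such findings at Screening or acquire a crown later.
- Administrative Change Letter #02 limits OHT to Screening and Day 56. From Day -14 or Day -28 to Day 56 is 56 + 14 = 70 to 56 + 28 = 84 days, or 68 to 86 days with the ±2-day window.
- The single-examiner requirement (Protocol 4.1 and 9.2) covers the two sensitivity measures. Section 9.3 assigns the safety examinations to trained clinical examiners in general. Two visual readings may therefore come from different people, and a present-to-absent reading without true change is possible.

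**3. Whether anything removes the entry afterwards**

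Protocol 12.2.7 and SAP 4.6.1 have all AEs reviewed before lock and coded. Neither states a step for deleting an entry that is not untoward. Treatment emergence depends on onset alone, so an entry dated on or after first use goes into the tables. With no OHT examination at Day 0, no examination can place a change before or after the acclimatization phase.

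**4. Scale**

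Input: about 52 randomized per arm (SAP 1.4), assuming all receive at least one dose and so enter the Safety population. If k subjects in an arm have such an entry as their only treatment-emergent AE, that arm's incidence rises by k/52:

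- k = 1: 1/52 = 1.9 percentage points
- k = 2: 2/52 = 3.8 points
- k = 3: 3/52 = 5.8 points

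These values of k are illustrative. A subject who has another treatment-emergent AE adds a row entry but does not raise overall incidence.

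**The case against.** The strongest reply is that the protocol already protects itself:

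- Section 10.4 ties reporting to events that meet the AE definition.
- Sections 10.5.1 and 10.5.2 require an intensity and a causality assessment for every AE, which a resolved finding could hardly receive.
- All AEs are reviewed before lock, and the OHT listing lets an odd entry be traced.
- Section 6.8 asks subjects to delay elective dental treatment. Work done on study should mostly be urgent, and the underlying condition would then be a legitimate AE under 10.1, only under a different term.

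Most of this stands as a limit on size. It does not remove the contradiction: 9.3.2 is the specific instruction for this examination, it is worded as mandatory, and no removal step is stated.

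Two broader readings are tempting, and the documents do not support them.

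- **Every listed appliance is a source of false AEs.** Exclusion criteria 19 and 20 bar partial dentures, braces and fixed retainers at entry, so in an eligible subject those items cannot go from present to absent.
- **The soft-tissue rule has a parallel fault.** A reader might infer this because 9.3.1 refers to Screening while the SAP says: "For all endpoints, the baseline value will be the Day 0 (Visit 2) pre-treatment assessment". But 9.3.1 records abnormality or worsening, not change. Section 10.1 also covers exacerbation of intermittent conditions, and SAP 3.1 sets a baseline for endpoints, which the soft-tissue examination is not. A Day 0 reference there would be a preference, not a correction.

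**Conclusion.** The point holds as a wording error with a small effect. As written, 9.3.2 records improvements, present-to-absent readings and dental work as AEs, contrary to 10.1 and unlike 9.3.1. Entries dated on or after first use would modestly inflate the treatment-emergent AE tables, by about 1.9 percentage points of an arm's incidence for each subject with no other such AE. That figure assumes 52 treated subjects per arm and a site that follows 9.3.2 literally.

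The number of affected subjects is not in the documents, and any rate would be a guess. It is probably small, given the limit on elective work and the overlap with legitimate AEs for underlying conditions.

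A reader might infer that the comparison of arms is biased or that the safety results cannot be relied on. Neither follows. The rule is identical in both arms and the examiner is blinded (Protocol 6.5), so the expected result is noise and some inflation in both arms. The efficacy analyses are not touched.

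**What to change.** In Protocol 9.3.2, replace the opening words *Any change* with *Any new abnormality or worsening of a pre-existing abnormality*. Add one sentence, consistent with 10.1: dental work is recorded as a treatment, and only the condition that led to it is recorded as an AE.

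The cost is two sentences of protocol text and matching CRF guidance, with no added examination, visit or staff. No change to the SAP tables is needed, because they take AEs as recorded.

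If Day 56 examinations have already begun, the blinded AE review before lock can check OHT-derived entries against 10.1, with any reclassification listed.

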9.3.3 Pregnancy Testing

For female subjects of childbearing potential, a UPT will be performed at Screening (Visit 1) and Baseline, and the results obtained prior to first use of acclimatization dentifrice (Visit 1) and first use of study dentifrice (Visit 2) respectively.

The investigator and site personnel will remind subjects at each visit to inform site personnel if their menstrual cycle has changed or if they have any other reason to suspect they may be pregnant (e.g. had unprotected intercourse since the last visit).

A negative pregnancy result is required before the subject may receive study product. Pregnancy tests will also be done whenever one menstrual cycle is missed during the active study period (or when potential pregnancy is otherwise suspected). Pregnancy tests may also be repeated as per request of the IRB/EC or if required by local regulations.

In the case of a positive confirmed pregnancy, the subject will be withdrawn from administration of study product and from the study.

10 ADVERSE EVENT AND SERIOUS ADVERSE EVENTS

10.1 Definition of an Adverse Event (AE)

An AE is any untoward medical occurrence in a clinical study subject, temporally associated with the use of a study product including any washout or lead-in product (or

medical device), whether or not considered related to the study product, including any washout or lead-in product (or medical device).

NOTE: An AE can therefore be any unfavorable and unintended sign (including an abnormal laboratory finding), symptom, or disease (new or exacerbated) temporally associated with the use of a study product including any washout or lead-in product (or medical device).

Events Meeting the AE Definition:

- Any abnormal laboratory test results (hematology, clinical chemistry, or urinalysis) or other safety assessments (e.g. ECG, radiological scans, vital sign measurements), including those that worsen from baseline, considered clinically significant in the medical and scientific judgment of the investigator (i.e., not related to progression of underlying disease).
- Exacerbation of a chronic or intermittent pre-existing condition including either an increase in frequency and/or intensity of the condition.
- New conditions detected or diagnosed after study product administration even though it may have been present before the start of the study.
- Signs, symptoms, or the clinical sequelae of a suspected drug-drug interaction.
- Signs, symptoms, or the clinical sequelae of a suspected overdose of either study product or a concomitant medication. Overdose per se will not be reported as an AE/SAE unless it is an intentional overdose taken with possible suicidal/self-harming intent. Such overdoses should be reported regardless of sequelae.
- "Lack of efficacy" or "failure of expected pharmacological action" per se will not be reported as an AE. Such instances will be captured in the efficacy assessments. However, the signs, symptoms, and/or clinical sequelae resulting from lack of efficacy will be reported as AE if they fulfill the definition of an AE.

Events NOT meeting the AE definition:

- Any clinically significant abnormal laboratory findings (if applicable) or other abnormal safety assessments which are associated with the underlying disease, unless judged by the investigator to be more severe than expected for the subject's condition.
- The disease/disorder being studied or expected progression, signs, or symptoms of the disease/disorder being studied, unless more severe than expected for the subject's condition.

- Medical or surgical procedure (e.g. endoscopy, appendectomy) is not the AE. The condition that leads to the procedure is an AE (e.g. appendicitis).
- Situations where an untoward medical occurrence did not occur (social and/or convenience admission to a hospital).
- Anticipated day-to-day fluctuations of pre-existing disease(s) or condition(s) present or detected at the start of the study that do not worsen.

10.2 Definition of a Serious Adverse Event (SAE)

A Serious Adverse Event (SAE) is a particular category of an adverse event where the adverse outcome is serious. If an event is not an AE per definition above, then it cannot be an SAE even if serious conditions are met (e.g. hospitalization for signs/symptoms of the disease under study, death due to progression of disease).

A serious adverse event is any untoward medical occurrence at any dose that:

- **Results in death**
- **Is life-threatening**
 - The term 'life-threatening' in the definition of 'serious' refers to an event in which the subject was at risk of death at the time of the event. It does not refer to an event, which hypothetically might have caused death, if it were more severe;
- **Requires inpatient hospitalization or prolongation of existing hospitalization**
 - In general, hospitalization signifies that the subject has been detained (usually involving at least an overnight stay) at the hospital or emergency ward for observation and/or treatment that would not have been appropriate in the physician's office or outpatient setting. Complications that occur during hospitalization are AEs. If a complication prolongs hospitalization or fulfills any other serious criteria, the event is serious. When in doubt as to whether "hospitalization" occurred, or was necessary, the AE should be considered serious.
 - Hospitalization for elective treatment of a pre-existing condition that did not worsen from baseline is not considered an AE.
- **Results in persistent or significant disability/incapacity**
 - The term disability means a substantial disruption of a person's ability to conduct normal life functions.

- This definition is not intended to include experiences of relatively minor medical significance such as uncomplicated headache, nausea, vomiting, diarrhea, influenza, and accidental trauma (e.g. sprained ankle) which may interfere with or prevent everyday life functions but do not constitute a substantial disruption
- **Results in congenital anomaly/birth defect**
- **Other situations:**
 - Medical or scientific judgment should be exercised in deciding whether SAE reporting is appropriate in other situations such as important medical events that may not be immediately life-threatening or result in death or hospitalization but may jeopardize the subject or may require medical or surgical intervention to prevent one of the other outcomes listed in the above definition. These events should usually be considered serious.
 - Examples of such events include invasive or malignant cancers, intensive treatment in an emergency room or at home for allergic bronchospasm, blood dyscrasias or convulsions that do not result in hospitalization, or development of drug dependency or drug abuse.

Note: Classification of an AE as 'serious' is based on the outcome of the event, and is a factor in determining reporting requirements.

10.3 Reporting of Adverse Events

10.3.1 Reporting Period

All AEs, and therefore all SAEs will be collected immediately after a subject consents to participate in the study by the completion (signature) of the ICF and until 5 days following last administration of the study product (or last procedure).

Medical occurrences that began before obtaining informed consent will be recorded in the Medical History/Current Medical Conditions section of the CRF not the AE section.

Details recorded by the subject on a diary or similar document that meet the definition of an AE must also be discussed with the subjects and transcribed in the AE section of the CRF.

10.4 Reporting Procedures

The investigator and any designees are responsible for detecting, documenting and reporting events that meet the definition of an AE and remain responsible for following

up on AEs that are serious, considered related to the study product(s), participation in the study, or a study procedure, or that caused the subject to discontinue the study product or study.

The investigator (or medically qualified designee) is to report all directly observed AEs and all AEs spontaneously reported by the study subject. In addition, each study subject will be questioned about AEs.

Each AE is to be assessed to determine if it meets the criteria for a SAE. If an SAE occurs, expedited reporting will follow local and international regulations, as appropriate.

When an AE occurs, it is the responsibility of the investigator (or medically qualified designee) to review all documentation (e.g. hospital progress notes, laboratory, and diagnostics reports) related to the event.

The investigator or site staff will then record all relevant information regarding an AE in the CRF and all details relating to an SAE in the paper SAE Form provided.

It is **not** acceptable for the investigator (or medically qualified designee) to send photocopies of the subject's medical records to GSK CH in lieu of completion of the AE CRF page/SAE form.

There may be instances when copies of medical records for certain cases are requested by GSK CH. In this instance, all subject identifiers, with the exception of the subject number, will be redacted on the copies of the medical records prior to submission to GSK CH.

The investigator (or medically qualified designee) will attempt to establish a diagnosis of the event based on signs, symptoms, and/or other clinical information. The diagnosis will be the documented as the AE/SAE where known and not the individual signs/symptoms. (e.g. upper respiratory tract infection, seasonal allergy, etc. instead of runny nose).

AEs elicited by the investigator (or medically qualified designee) in a standard manner at the study visits should also be recorded in the AE section of the CRF and/or using the SAE form (subject to the classification of the AE). Care will be taken not to introduce bias when questioning a subject about any changes in their health. Open-ended and non-leading verbal questioning should be used.

